7.3. Analysis of the Efficacy Parameters

7.3.1. Primary Efficacy Analysis

Objective response rate is defined as the proportion of participants with at least 1 confirmed response of CR, VGPR, or PR, according to IMWG criteria.

Objective response rate in Phase 2 was the planned primary endpoint. Due to the small number of participants in Phase 2, only listings of the response assessment data will be provided. Therefore, ORR will not be calculated and will not be presented in the CSR.

The IMWG criteria are presented in [Table 2](#). Per IMWG uniform response criteria, all response categories and PD require 2 consecutive assessments except for radiographic or bone marrow assessments. If a participant discontinues treatment without a PD, receives a subsequent anticancer therapy and then responds, this will not be included as a responder for ORR.

Table 2: International Uniform Response Criteria Consensus Recommendations

Response	Response Criteria
sCR	
• CR as defined below, plus• Normal FLC ratio, and• Absence of clonal PCs by immunohistochemistry, immunofluorescence,^a or 2- to 4-color flow cytometry
CR ^b	
• Negative immunofixation on the serum and urine, and• Disappearance of any soft tissue plasmacytomas, and• < 5% PCs in bone marrow
VGPR ^b	
• Serum and urine M-component detectable by immunofixation but not on electrophoresis, or• ≥ 90% reduction in serum M-protein plus urine M-protein < 100 mg/24 hours

Table 2: International Uniform Response Criteria Consensus Recommendations (Continued)

Response	Response Criteria
PR	
 • $\geq 50\%$ reduction of serum M-protein and reduction in 24-hour urinary M-protein by $\geq 90\%$ or to $< 200 \text{ mg/24 hours}$ • If the serum and urine M-protein are not measurable, a decrease of $\geq 50\%$ in the difference between involved and uninvolved FLC levels is required in place of the M-protein criteria • If serum and urine M-protein are not measurable, and serum free light assay is also not measurable, $\geq 50\%$ reduction in bone marrow PCs is required in place of M-protein, provided baseline bone marrow PC percentage was $\geq 30\%$ • In addition to the above criteria, if present at baseline, a $\geq 50\%$ reduction in the size (SPD) of soft tissue plasmacytomas is also required
MR	
 • $\geq 25\%$ but $\leq 49\%$ reduction of serum M-protein and reduction in 24-hour urine M-protein by 50% to 89% • In addition to the above criteria, if present at baseline, 25% to 49% reduction in the size of soft tissue plasmacytomas is also required • No increase in size or number of lytic bone lesions (development of compression fracture does not exclude response)
SD	
 • Not meeting criteria for CR, VGPR, PR, MR, or PD
PD ^c	
Increase of 25% from lowest response value in any one of the following:
 
 • Serum M-component (absolute increase must be $\geq 0.5 \text{ g/dL}$) • Urine M-component (absolute increase must be $\geq 200 \text{ mg/24 hours}$) • Only in participants without measurable serum and urine M-protein levels: the difference between involved and uninvolved FLC levels (absolute increase must be $> 10 \text{ mg/dL}$) • Only in participants without measurable serum and urine M-protein levels and without measurable disease by FLC levels, bone marrow PC percentage (absolute percentage must be $\geq 10\%$) • Bone marrow PC percentage: the absolute percentage must be $> 10\%$ • Definite development of new bone lesions or soft tissue plasmacytomas or definite increase in the size of existing bone lesions or soft tissue plasmacytomas (SPD) • Development of hypercalcemia (corrected serum calcium $> 11.5 \text{ mg/dL}$) that can be attributed solely to the PC proliferative disorder

Note: All response categories (CR, sCR, VGPR, PR, and PD) require 2 consecutive assessments made at any time before the institution of any new therapy; CR, sCR, VGPR, PR, and SD categories also require no known evidence of progressive or new bone lesions if radiographic studies were performed. VGPR and CR categories require serum and urine studies regardless of whether disease at baseline was measurable on serum, urine, both, or neither.

Note: Radiographic studies are not required to satisfy these response requirements. Bone marrow assessments need not be confirmed. For PD, serum M-component increases of more than or equal to 1 g/dL are sufficient to define relapse if starting M-component is $\geq 5 \text{ g/dL}$.

^a Presence/absence of clonal cells is based upon the kappa/lambda ratio. An abnormal kappa/lambda ratio by immunohistochemistry or immunofluorescence requires a minimum of 100 PCs for analysis. An abnormal ratio reflecting presence of an abnormal clone is kappa/lambda of $> 4:1$ or $< 1:2$.

^b Clarifications to IMWG criteria for coding CR and VGPR in participants in whom the only measurable disease is by serum FLC levels: CR in such participants indicates a normal FLC ratio of 0.26 to 1.65 in addition to CR criteria listed above. VGPR in such participants requires a $> 90\%$ decrease in the difference between involved and uninvolved FLC levels.

^c Clarifications to IMWG criteria for coding PD: Bone marrow criteria for PD are to be used only in participants without measurable disease by M-protein and by FLC levels; "25% increase" refers to M-protein, FLC, and bone marrow results, and does not refer to bone lesions, soft tissue plasmacytomas, or hypercalcemia, and the "lowest response value" does not need to be a confirmed value.

7.3.2. Secondary Efficacy Analyses

7.3.2.1. Best Overall Response

The best overall response, according to IMWG criteria, will be listed for each participant in the FAS.

7.3.2.2. Time to Response

Time to response is defined as the number of days from the randomization in Phase 2 (or first dose of study drug in Phase 1) to the first documented response of PR, VGPR, or CR (as per IMWG criteria). Time to response will be listed for the FAS.

7.3.2.3. Duration of Response

Duration of response is defined as the number of days from earliest date of PR, VGPR, or CR (as per IMWG criteria) until the earliest date of disease progression, relapse, or death due to any cause. Duration of response will be listed for the FAS.

7.3.2.4. Progression-Free Survival

Progression-free survival is defined as the number of days from the date of first dose of study drug in Phase 1 (or from randomization date in Phase 2) until either PD, as per IMWG criteria, or death, whichever occurs first.

Censoring rules for PFS are described in [Table 3](#).

Table 3: Evaluation and Censoring of Progression-Free Survival

Situation	Outcome	Date of Progression or Censoring
No baseline tumor assessments	Censored	Date of randomization or Day 1 (for Phase 1)
No valid postbaseline response assessments	Censored	Date of randomization or Day 1 (for Phase 1)
Progression documented between scheduled response assessments	Progressed	Date of first overall response of PD
No progression	Censored	Date of last valid efficacy/disease assessment (not NE and not missing)
Study withdrawal for undocumented progression	Censored	Date of last valid efficacy/disease assessment (not NE and not missing)
Study withdrawal for toxicity or other reason	Censored	Date of last valid radiologic assessment (not NE and not missing)
New anticancer treatment started	Censored	Date of last valid efficacy/disease assessment (not NE and not missing) on/before starting a new anticancer treatment
Death before first progressive response assessment	Progressed	Date of death
Death between adequate response assessments	Progressed	Date of death
Death or progression after 2 or more missed assessments	Censored	Date of last valid efficacy/disease assessment (not NE and not missing)

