Serum calcium corrected for albumin	X	X				X		X	X	X	X	X	X	See Section 8.2.1.3 .
Serum FLC & serum/urine immunofixation	X	X*				X*		X*	X*	X*	X*	X*	X*	To be performed when CR is suspected or maintained. * For participants with light chain only disease, serum FLC to be performed on Day 1 of each cycle, at EOT, and at safety and disease status follow-up. See Section 8.2.1.2 .
Efficacy/disease assessments (other)														
Bone marrow aspirate/biopsy for assessment of MRD [REDACTED]	X*	Samples are requested at the time of suspected CR to confirm CR/sCR and to evaluate MRD. [REDACTED] [REDACTED]						X**						Bone marrow samples to be collected at screening (up to 42 d before C1D1). *In the event a fresh screening biopsy will not be collected, use non-decalcified diagnostic tissue (ie, bone marrow aspirate slides or FFPE tissue). ** If feasible, collect at disease progression for participants who achieved PR/CR. See Sections 8.5.8 and 8.2.1.6 .
Skeletal survey	X*	As clinically indicated												*For screening, up to 42 d before C1D1. See Section 8.2.1.7 .
Assess extramedullary plasmacytomas	X*	Measurable sites every 4 weeks (if applicable; for physical examination) and every 12 weeks** (for radiologic examination) for participants with a history of plasmacytomas, or as clinically indicated for others.												*For screening, up to 42 d before C1D1. ** At 18 months after the participant's first dose, the timing of radiologic assessment of extramedullary plasmacytomas should follow the standard of care. See Section 8.2.1.8 .

Table 4: Schedule of Activities for Participants in Phase 2, Treatment Group B – Part 2 and Treatment Group C – Part 2 (Who Cross Over)

Visit Day (Range)	Treatment (28-day Cycles)							EOT	Follow-Up			Notes
	Cycles 1 and 2				Cycles 3 to 6		Cycles 7+		Safety	Disease Status	Survival	
	D1	D8 (± 2d)	D15 (± 2d)	D22 (± 2d)	D1 (± 3d)	D15 (± 3d)	D1 (± 3d)	+ 7d	28-35d After EOT	Q8W After EOT ± 7d	Q12W After EOT ± 7d	
Administrative procedures												
Review criteria for crossover	X											
Concomitant medications	X	X	X	X	X	X	X	X				See Section 6.8.
Distribute reminder cards	X	X	X	X	X	X	X					See Section 8.1.4.
Assess study treatment compliance	X*				X		X	X				* C2D1 only. See Section 6.4.
Study treatment												
Dispense/administer INCB001158	X	X	X	X	X	X	X					In clinic, should be given just before administration of daratumumab SC. See Section 6.1, Appendix B, and refer to the Pharmacy Manual.

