8.2. Efficacy Assessments

NOTE: As of Protocol Amendment 3, the disease assessments are only required to be performed as per the site standard of care guidelines for the participant's condition and monitoring.

Participants must be withdrawn from the study if, in the opinion of the investigator, the disease has progressed and the participant is no longer having clinical benefit from the study treatment.

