8.2.1. Evaluations

8.2.1.1. Responses Categories

Assessment of tumor response and disease progression will be conducted in accordance with the IMWG response criteria. Disease evaluations will include measurements of myeloma proteins, bone marrow examinations, skeletal surveys, assessment of extramedullary plasmacytomas, and measurements of serum calcium corrected for albumin.

Efficacy/disease evaluations must be performed at each treatment cycle as specified in the SoA (see [Table 3](#) and [Table 4](#); as of Protocol Amendment 3, see [Table 7](#) for all participants). The sponsor may request that the disease assessments be sent for central independent review. Disease evaluations scheduled for treatment days should be collected before study treatment is administered. Disease evaluations will be performed by a central laboratory (unless otherwise

specified) until disease progression or the EOT. This study will use the IMWG consensus recommendations for MM treatment response criteria (Durie et al 2006, Kumar et al 2016, Rajkumar et al 2011) presented in [Table 19](#). Per IMWG uniform response criteria, all response categories and PD require 2 consecutive assessments except for radiographic or bone marrow assessments. For quantitative Ig at baseline, M-protein, IFE, and FLC measurements in serum and 24-hour urine, the investigator will use results provided by the central laboratory. For participants with suspected daratumumab interference on SPEP and IFE, a reflex assay will be performed (see [Appendix E](#)). Participants with confirmed daratumumab interference who meet all other clinical criteria for CR or sCR will be considered CR/sCR.

Table 19: International Uniform Response Criteria Consensus Recommendations

Response	Response Criteria
Stringent complete response (sCR)	
• CR as defined below, plus• Normal FLC ratio, and• Absence of clonal PCs by immunohistochemistry, immunofluorescence,^a or 2- to 4-color flow cytometry.
Complete response (CR) ^b	
• Negative immunofixation on the serum and urine, and• Disappearance of any soft tissue plasmacytomas, and• < 5% PCs in bone marrow.
Very good partial response (VGPR) ^b	
• Serum and urine M-component detectable by immunofixation but not on electrophoresis, or• ≥ 90% reduction in serum M-protein plus urine M-protein < 100 mg/24 hours.

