8.2.1.7. Assessment of Lytic Disease

A complete skeletal survey (including skull, entire vertebral column, pelvis, chest, humeri, femora, and any other bones for which the investigator suspects involvement by disease) is to be performed and evaluated by the local laboratory by roentgenography (or the local standard of care imaging, eg, low-dose whole body CT) during the screening period. Please note that the same methodology used at screening should be used throughout the study for comparison purposes. During the treatment period and before disease progression is confirmed, imaging should be performed whenever clinically indicated based on symptoms or to document response or progression. Magnetic resonance imaging is an acceptable method for evaluation of bone disease and may be included as an additional assessment at the discretion of the investigator (see the disease response criteria in [Table 19](#)).

Participants may show disease progression manifested by symptoms of pain due to bone changes. Therefore, disease progression may be documented, in these cases, by skeletal survey or other radiographs, depending on the symptoms that the participant experiences. If the diagnosis of disease progression is obvious by radiographic investigations, then no repeat confirmatory imaging is necessary. In instances where changes may be subtler, repeat imaging may be performed in 1 to 3 weeks according to investigator discretion.

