7.1. General Considerations

The primary endpoint of the Phase 2 portion of the Protocol is ORR, defined as the proportion of participants with CR, VGPR, or PR, according to IMWG criteria in the randomized FAS. Due to the small sample size of participants enrolled in Phase 2 at the time of study termination, only listings of the efficacy data will be provided.

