3.2.8	Summary of Treatment-Emergent Adverse Events Leading to INCB001158 Dose Reduction by MedDRA Preferred Term in Decreasing Order of Frequency	FAS	
3.2.9	Summary of Treatment-Emergent Adverse Events Leading to INCB001158 Dose Interruption by MedDRA Preferred Term in Decreasing Order of Frequency	FAS	
3.2.10	Summary of Treatment-Emergent Adverse Events Leading to Discontinuation of INCB001158 by MedDRA Preferred Term in Decreasing Order of Frequency	FAS	
3.3.1.1	Summary of Laboratory Values - Hematology	FAS	X
3.3.1.2	Summary of Laboratory Values - Chemistry	FAS	X
3.3.3.4	Treatment-Emergent Worsening of Laboratory Abnormalities - Hematology	FAS	X
3.3.3.5	Treatment-Emergent Worsening of Laboratory Abnormalities - Chemistry	FAS	X
3.4.1	Summary of Systolic Blood Pressure	FAS	X
3.4.2	Summary of Diastolic Blood Pressure	FAS	X
3.4.3	Summary of Pulse	FAS	X
3.4.4	Summary of Respiratory Rate	FAS	X
3.4.5	Summary of Body Temperature	FAS	X
3.4.6	Summary of Body Weight	FAS	X
3.5.1	Summary of PR Interval (ms) From 12-Lead ECG	FAS	X
3.5.2	Summary of QRS Interval (ms) From 12-Lead ECG	FAS	X
3.5.3	Summary of QT Interval (ms) From 12-Lead ECG	FAS	X
3.5.4	Summary of QTcF Interval (ms) From 12-Lead ECG	FAS	X
3.5.5	Summary of RR Interval (ms) From 12-Lead ECG	FAS	X
3.5.6	Summary of Heart Rate (bpm) From 12-Lead ECG	FAS	X
3.5.7	Summary of Outliers of QT and QTcF Interval Values (ms) From 12-Lead ECG	FAS	X

Listings

Listing No.	Title
2.1.2.x	Participant Enrollment and Disposition Status
2.2.1.x	Participant Inclusion and Exclusion Criteria Violations
2.2.2.x	Protocol Deviations
2.3.1.x	Analysis Populations
2.4.1.x	Demographics and Baseline Characteristics
2.4.2.x	Baseline Disease Characteristics
2.4.3.x	Prior Radiation Treatment
2.4.4.x	Prior Therapy for Disease Under Study
2.4.5.x	Prior Surgery or Surgical Procedure
2.4.6.x	Medical History
2.4.7.x	Prior and Concomitant Medications
2.4.8.x	Post-Treatment Anticancer Therapy
2.5.1.x	Study Drug Administration for INCB001158
2.5.2.x	Study Drug Compliance for INCB001158
2.5.3.x	Study Drug Administration for Daratumumab SC
2.6.1.x	Overall Response Assessments and Best Overall Response Under IMWG Criteria
2.6.2.x	Efficacy Endpoints (TTR, DoR, PFS, and OS)
2.6.3.x	ECOG Status
2.6.4.x	Clinical Laboratory Values – Chemistry, SPEP
2.6.5.x	Clinical Laboratory Values – Immunology
2.6.6.x	Clinical Laboratory Values – Immunology, Free Light Chains
2.6.7.x	Clinical Laboratory Values – Immunology, Immunofixation

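### One row of SAP Table 3 censors PFS at the last radiologic assessment, which conflicts with the no-progression row and can put a listed PFS date before Day 1

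*SAP*

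**What the plan says.** SAP Section 7.3.2.4 counts PFS from first dose of study drug in Phase 1 and from randomization in Phase 2. Table 3 then gives the censoring dates. Five rows censor at a last valid assessment:

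- Four of them (no progression; withdrawal for undocumented progression; start of new anticancer treatment; death or progression after two or more missed assessments) use "Date of last valid efficacy/disease assessment (not NE and not missing", with the added limit of on or before the new treatment in the third.
- The row for study withdrawal because of toxicity or another reason uses "Date of last valid radiologic assessment (not NE and not missing".

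Two further rows, for no baseline assessment and for no valid postbaseline response assessment, censor at randomization or Day 1. The table states no order of precedence among its rows.

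On the assessment schedule, Protocol Section 8.2.1.1 says "Efficacy/disease evaluations must be performed at each treatment cycle as specified in the SoA". Protocol Table 3 places SPEP and UPEP on Day 1 of each cycle. The skeletal survey footnote in that table reads "For screening, up to 42 d before C1D1". After screening, Protocol Section 8.2.1.7 says "imaging should be performed whenever clinically indicated based on symptoms or to document response or progression". Imaging at a fixed interval, about every 12 weeks, applies only to participants with a history of plasmacytomas (Protocol Section 8.2.1.8). The notes to SAP Table 2 add that response can be established without radiographic studies.

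On outputs, SAP Section 7.1 says "only listings of the efficacy data will be provided". Appendix A keeps PFS in Listing 2.6.2.x, "Efficacy Endpoints (TTR, DoR, PFS, and OS".

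**The concern.** A radiologic censoring date belongs to a trial in which scans drive the progression assessment. Here M-protein does, and for many participants the screening survey may be the only imaging on file. Three problems follow.

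- **A date before time zero.** The cell qualifies the assessment only as evaluable and not missing. Nothing limits it to assessments after baseline, so a screening survey can supply the censoring date.
- **Two dates for one participant.** Someone who withdraws for toxicity without progression also meets the no-progression row, which gives a different date.
- **A reversed ordering.** A participant with many valid M-protein assessments can be censored earlier than one with none, who is censored at Day 1 in Phase 1. The no-postbaseline row cannot rescue the first participant, because valid postbaseline assessments do exist.

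What is at stake is whether the per-participant PFS values in Listing 2.6.2.x are correct and reproducible. They could be negative, too short, or dependent on which row the programmer applies.

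**Working it through.** The documents give no figure on this point to reproduce. The check applies the competing rows to the same participant.

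**Inputs**
- Time origin: first dose, Day 1, in Phase 1 (SAP 7.3.2.4), counted as 0.
- Disease assessment on Day 1 of each 28-day cycle (Protocol Table 3, Section 8.2.1.1).
- Screening skeletal survey 1 to 42 days before Day 1 (Protocol Table 3). Study day -1 is one day before Day 1 (SAP 4.1.2).
- Assumptions: nominal visit days, the schedule in force before Amendment 3, and no clinically indicated scan on study.

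**Formulas**
- No-progression row: PFS = 28 × (c - 1), where the last valid assessment is at Cycle c Day 1.
- Withdrawal row with screening imaging only: PFS = -42 to -1.
- Difference = 28 × (c - 1) + 1 to 28 × (c - 1) + 42.

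The SAP does not say whether 1 day is added to PFS. Adding it shifts both dates equally and leaves the difference unchanged; the withdrawal row would then give -41 to 0.

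**Results in days, Phase 1**

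| Last valid assessment | No-progression row | Withdrawal row | Difference |
|---|---|---|---|
| C2D1 | 28 | -42 to -1 | 29 to 70 |
| C3D1 | 56 | -42 to -1 | 57 to 98 |
| C6D1 | 140 | -42 to -1 | 141 to 182 |
| C7D1 | 168 | -42 to -1 | 169 to 210 |

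For C7D1: 28 × 6 = 168; 168 - (-1) = 169; 168 - (-42) = 210. A Phase 1 participant with no valid postbaseline assessment is censored at 0.

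**Participants with plasmacytoma imaging every 12 weeks**
- From the first on-treatment scan: scans at days 84, 168 and so on, against assessments at 84, 112, 140 and 168, leave gaps of 0, 28 or 56 days.
- Before that scan, with the last assessment at day 28 or 56: 28 - (-1) = 29 to 56 - (-42) = 98 days.

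**Phase 2.** The origin is randomization. The interval from randomization to first dose is not stated. If it is 0 to 7 days (an assumption), a survey 42 days before first dose gives -42 to -35 days.

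**The case against.** The strongest reply is that a valid assessment in this table naturally means a postbaseline one. A screening survey yields no response category, and the first two rows suggest that time zero was meant as the floor. On that reading the date is never negative. But the SAP defines validity only as evaluable and not missing, and on the narrower reading a participant without on-study imaging has no date at all. The row fails either way, so only the form of the failure is open.

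It can also be said that a specific row normally overrides a general one. That would settle the precedence question, but in favor of the row with the wrong date. The row for new anticancer treatment also overlaps the no-progression row; the change proposed here does not touch that overlap.

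On size, the protocol limits screening to 28 days (Section 8.1.2), which would lower the upper difference in the C7D1 example to 168 + 28 = 196 days. The footnote for imaging, however, expressly allows 42 days. Scans done when clinically indicated, or to document response, would narrow the gap; the figures above are for participants without them.

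Two limits stand. First, before Amendment 3 a participant who stopped treatment for toxicity went into disease status follow-up (Protocol Section 8.8.2) and did not thereby leave the study, which reduces the number meeting this row. Second, nothing inferential depends on PFS. The response assessments and M-protein results are listed separately, so a reader could find the last assessment, and a negative value would be easy to notice.

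**Conclusion.** The point holds and is minor. One cell of SAP Table 3 uses the wrong type of assessment for this disease and schedule. It conflicts with the no-progression row and, read literally, allows a PFS censoring date before Day 1. In the C7D1 example the two rows differ by 169 to 210 days. With 12-weekly plasmacytoma imaging the gap is 0, 28 or 56 days from the first on-treatment scan and 29 to 98 days before it.

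These figures assume nominal visits, the schedule before Amendment 3 and no clinically indicated imaging. Under Amendment 3, "the disease assessments are only required to be performed as per the site standard of care guidelines", so later gaps depend on site practice. The number of participants in this row is not given. The consequence is limited to individual values in Listing 2.6.2.x; no summary, estimate or test of PFS is planned.

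**What to change.** In SAP Table 3, in the row for study withdrawal because of toxicity or another reason, replace the last valid radiologic assessment with the last valid efficacy/disease assessment, keeping the condition that it is neither NE nor missing. The row then gives the same date as the no-progression row, so no precedence rule between those two is needed. A participant with valid postbaseline assessments can then no longer be dated before Day 1 by this row.

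The cost is one table cell; the data are already collected. If Listing 2.6.2.x has already been programmed, the derivation actually used for these participants should be recorded.
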